3.8 Primary endpoint

28 days after randomization.

3.9 Comprehensive therapy

The treatment of COVID-19 is followed by the CDC protocol. Comprehensive therapy is provided by the ICU attending physicians based on published ARDS guidelines. Antivirus treatment and the use of steroids will be recorded as well.

4. CHARACTERISTICS OF DATA/SPECIMENS TO BE ANALYZED

4.1. Data collection

The following information of all patients is collected in a data file: patients' characteristics, including age, gender, medical history, diagnosis for COVID-19, the laboratory and microbiology findings, treatment and outcome. Complications including skin breakdown, IV line or nasal cannula dislodgement or desaturation during position change. The respiratory assessments before, during the treatments of HFNC or HFNC with prone position.

4.2. Statistical analysis

Definition of the two groups: The patients who receive the prone positioning are classified as prone positioning group. The patients who receive HFNC alone are classified as HFNC group.

Comparisons between the two groups: Quantitative continuous variables are given as either means (\pm SDs) or medians (with inter-quartile ranges) are compared using the unpaired Student's t test or the Mann-Whitney test. Qualitative or categorical variables are compared with the chi-square test or the Fisher's exact test. ANOVA for paired tests to compare the same variables collected at different time points are used. The cumulative probability of remaining on spontaneous breathing are compared with the Kaplan-Meier estimate of survival and the log-rank test to compare the two groups. Univariate and multivariate analyses of risk factors for PP failure

are performed with logistic regression. All analyses are in intention to treat, and the level of significance is set at 0.05.

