2.2. Exclusion criteria

The exclusion criterion are

- 1) If the patients have a consistent $SpO_2 < 80\%$ when on evaluation with a FiO_2 of 0.6, or signs of respiratory fatigue ($RR > 40/\text{min}$, $PaCO_2 > 50\text{mmHg}$ / $pH < 7.30$, and obvious accessory respiratory muscle use);
- 2) Immediate need for intubation ($PaO_2/FiO_2 < 50\text{mmHg}$ or $SpO_2/FiO_2 < 90$, unable to protect airway or mental status change);
- 3) Hemodynamic instability (sustained $SBP < 90\text{mmHg}$, sustained MBP below 65 mmHg or requirement for vasopressor);
- 4) Unable to collaborate with HFNC/PP with agitation or refuse HFNC/PP.
- 5) Chest trauma or any contraindication for PP
- 6) Pneumothorax
- 7) Age < 18 years
- 8) Pregnant
- 9) Unable to communicate
- 10) Severe obese ($BMI \geq 40$)
- 11) Patient self-proned for more than an hour

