3.2. Randomization and masking

Randomization will be stratified on ARDS severity (moderate and severe) performed by permuted block methods using Fisher and Yates tables of random permutations using a centralized interactive contact system is used for randomization. The random block length is 4, and random numbers are generated by computer. All of the centers participating in this study are immediately put in contact with the central unit (Rush University Medical Center) to obtain a randomization number if a patient fulfills the inclusion criteria. Within 6 hr of fulfilling inclusion criteria, a patient will be randomly allocated either to the prone positioning group or the control group (HFNC alone with no prone positioning therapy).

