3.3. Blinding and Quality Control

The trial will be overseen by a steering committee, and data quality control will be completed by independent data monitoring board. Clinicians and epidemiologists of above organization are not members of participating in our research group. Research coordinator will timely verify database and regularly monitored all the centers on site to ensure the accuracy of

the data recorded. An investigator at each center is responsible for enrolling patients in the study, ensuring adherence to the protocol, and completing the electronic case-report form. Although the individual study assignments of the patients could not be blinded, the coordinating center and all the investigators will remain unaware of the study group outcomes until the data are unlocked. All the analyses are performed by the study statistician not involved in study recruitment, and blind of randomization group until database lock.

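### Section 4.2 defines the compared groups by treatment received, against the random allocation in 3.2 and the intention-to-treat statement in 4.2 itself

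*Combined protocol and SAP*

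**What the plan says.** Section 4.2 opens with a labelled definition of the two groups: "The patients who receive the prone positioning are classified as prone positioning group" and "The patients who receive HFNC alone are classified as HFNC group". Its next paragraph sets out the tests comparing the two groups. The section ends: "All analyses are in intention to treat, and the level of significance is set at 0.05".

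Section 3.2 forms the groups differently: each patient is "randomly allocated either to the prone positioning group or the control group (HFNC alone with no prone positioning therapy"). Section 3.3 says the statistician stays "blind of randomization group until database lock".

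No section says which rule prevails. None names a separate as-treated or per-protocol set, or says where to count a prone-arm patient who is never proned or a control who is proned.

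**The concern.** The first two sentences of 4.2 are an as-received rule, and the last is an as-randomised rule. They classify two kinds of patient differently:

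- a patient assigned to prone positioning who is never proned (prone group by allocation, HFNC group by receipt);
- a control who is proned (HFNC group by allocation, prone group by receipt).

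Both can occur. Under section 3.4 the patient carries out the proning, and section 3.3 accepts that assignment cannot be blinded. Whether a patient is proned after randomisation may depend on how ill that patient is. Someone who deteriorates before the first session is a likely intubation, and the literal rule would move that event from the prone arm to the control group. The comparison would then no longer be protected by randomisation. The bias could run either way, depending on who crosses over.

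**Working it through.** **1. The plan's own figure.** Section 4.3 gives 60% versus 45% intubation, 95% confidence and 80% power. Assuming 1:1 allocation and a two-sided test (neither is stated), with pooled variance and mean rate 0.525:

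n per arm = [1.960·√(2·0.525·0.475) + 0.842·√(0.60·0.40 + 0.45·0.55)]² / 0.15² = 172.8, so 173 per arm and 346 in total. This matches the plan. The total has no stated allowance for crossover, and the choice of group definition does not change it.

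**2. Set-up for the illustration.** From the documents: 173 per arm, a 60% event rate and a 5% level. Assumed, because the documents are silent: no true effect (60% in both randomised arms), *m* prone-arm patients never proned, and event rate *q* among them. The proned patients' rate is set so that the prone arm stays at 60% overall. The test is Pearson chi-square without continuity correction, two-sided.

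Expected rates under the as-received rule:

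- prone group: (173·0.60 − m·q) / (173 − m)
- HFNC group: (173·0.60 + m·q) / (173 + m)

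For m = 17 and q = 75%, the prone group is (103.8 − 12.75)/156 = 58.4% and the HFNC group is (103.8 + 12.75)/190 = 61.3%. That is a spurious 3.0-point benefit.

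**3. False-positive rates**, by exact enumeration of the binomial outcomes:

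| Never proned | q | Prone vs HFNC, as received | Rejection rate |
|---|---|---|---|
| 17 of 173 (9.8%) | 60% | 60.0% vs 60.0% | 5.0% |
| 17 | 75% | 58.4% vs 61.3% | 8.7% (8.1 favouring prone) |
| 17 | 90% | 56.7% vs 62.7% | 20.1% (20.0 favouring prone) |
| 17 | 45% | 61.6% vs 58.7% | 8.6% (8.1 favouring HFNC) |
| 9 of 173 (5.2%) | 60% | 60.0% vs 60.0% | 5.1% |
| 9 | 75% | 59.2% vs 60.7% | 6.1% |
| 9 | 90% | 58.4% vs 61.5% | 9.2% |
| 9 | 45% | 60.8% vs 59.3% | 6.0% |

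With 3 of 173 never proned, the rate is 5.0–5.4% across these values of q. Analysing the eight tabled cases by randomised arm gives 4.9–5.2%.

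**4. Proned controls.** With 17 never proned and 17 proned controls, all at a 75% event rate, the shifts cancel and the rate returns to about 5%. With 17 never proned and 9 proned controls it is 5.7% when both have 75% events and 7.8% when both have 90%. With 17 proned controls alone at 75% it is 8.7%, with 8.1 favouring HFNC.

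**5. Direction when there is a true effect.** At 60% versus 45% with m = 17, the as-received difference is (103.8 + 17q)/190 − (77.85 − 17q)/156 = 0.0473 + 0.1984q. It equals the true 0.15 at q ≈ 51.8%. Above that, the literal rule overstates the benefit of proning; below it, the rule understates it. At q = 50% the difference is 14.7 points.

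**The case against.** The best defence is that receiving a treatment is loose wording for being assigned to it. Section 4.2 reuses the arm labels of 3.2, section 3.3 speaks of the randomisation group, and the intention-to-treat sentence admits no exception. On that reading nothing is biased. This is probably what was meant. But 3.2 describes how patients are allocated, not how they are classified for analysis. The only sentences labelled as the group definition use receipt, and the tests follow directly from them.

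The second defence is that few patients would move. The definition sets no minimum duration, so anyone who starts one session stays in the prone group under either rule. Intolerance or side effects during proning under 3.6 therefore do not by themselves cause reclassification. Section 2.2 also screens out, before randomisation, patients who are "Unable to collaborate with HFNC/PP with agitation or refuse HFNC/PP", those with "Immediate need for intubation", and any "Patient self-proned for more than an hour". This stands as a reason to expect mismatches to be limited. It does not remove them, since a patient can refuse, deteriorate or self-prone after randomisation.

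Third, the largest figure (20.1%) needs about 10% never proned, a 90% event rate among them and no proned controls. That is true, so it is one end of a range and not a forecast.

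**Conclusion.** The concern holds. As written, 4.2 contains two incompatible rules for who is compared with whom, and the explicit definition is the one that departs from randomisation. The contradiction is certain; its numerical effect is not. If intention to treat is followed, the effect is nil. If the definition is followed, the false-positive rate ranges from about 5% when mismatches are rare or balanced to about 20% in the most adverse case computed, and the bias can favour either arm. These figures assume no true effect, 60% events, 173 per arm, and crossover and event rates that the documents do not supply. It should be fixed, because an analysis plan should not leave this choice open until after unblinding.

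**What to change.** Replace the definition in 4.2 with: *Patients are analysed in the group to which they were randomised (HFNC+PP or HFNC alone), regardless of prone positioning received.* Label any as-received analysis as a sensitivity analysis.

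A related gap can be closed at the same time. Section 3.6 does not say whether patients who meet a withdrawal criterion stay in follow-up to the 28-day endpoint in section 3.8 (Primary endpoint). State there that they do, and that they are analysed in their assigned arm, as the declared intention-to-treat analysis already requires.

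The cost is one sentence in each section, agreed before the data are unlocked. There are no extra patients or procedures, and the total stays at 346.

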1.3. Primary Objectives

The primary outcome for the efficacy of PP combined with HFNC will be the treatment failure rate and intubation rate of HFNC or HFNC+PP support and clinical requirement for advanced respiratory support including NIV, invasive ventilation or ECMO.

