2. STUDY METHODS

This is a multi-center randomized controlled trial, which will be approved by the Ethic Committees of all the participant hospitals. This trial is registered with ClinicalTrials.gov (NCT04325906).

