3.8 Treatment Failure Criteria

Failure criteria: treatment failure is defined as one of the following criteria¹⁷:

(1) Signs of persisting or worsening respiratory failure, defined by at least two of the following criteria:

- Respiratory rate above 40 cycles/min
- Lack of improvement of signs of respiratory-muscle fatigue
- Development of copious tracheal secretions
- Respiratory acidosis with a pH below 7.35
- SpO₂ below 90% at F_IO₂ ≥ 0.8 for more than 5 min without technical dysfunction

(2) Hemodynamic instability defined by a SBP below 90 mmHg, MBP below 65 mmHg or requirement for vasopressor;

(3) Deterioration of neurologic status (with a Glasgow coma scale below 12 points).

For patients who meet the failure criteria in the HFNC and HFNC+PP groups, a trial of NIV might be allowed according to the physician's preference in patients with signs of persisting or worsening respiratory failure and no other organ dysfunction before performing endotracheal intubation and invasive ventilation. Reasons for intubation will be recorded as well.

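### The between-arm tests ignore ARDS severity (the randomisation stratum), centre and baseline predictors already collected: valid, but modest power is given up

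*Combined protocol and SAP*

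**What the plan says.** Section 2 describes the design: "This is a multi-center randomized controlled trial". The number and size of centres are not given. Section 3.2 gives the allocation method: "Randomization will be stratified on ARDS severity (moderate and severe) performed by permuted block methods", run from one central unit, and "The random block length is 4". Centre is not a stratification factor.

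Section 1.3 sets the primary outcome as "the treatment failure rate and intubation rate of HFNC or HFNC+PP support", together with the need for more advanced respiratory support. The horizon is "28 days after randomization" (section 3.8, Primary endpoint).

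For comparisons between arms, section 4.2 lists t or Mann-Whitney tests for continuous variables and Kaplan-Meier curves with a log-rank test. For binary outcomes it says: "Qualitative or categorical variables are compared with the chi-square test or the Fisher's exact test". None of these is stratified or adjusted. The only regression is a logistic analysis of risk factors for failure of prone positioning, which is not the randomised comparison.

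Baseline information is planned: "patients' characteristics, including age, gender, medical history" (section 4.1), and vital signs before and during HFNC (section 3.5).

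**The concern.** Severity was thought important enough to stratify on, yet it drops out of every test between arms. If severity predicts failure, balancing on it and then ignoring it makes the unadjusted test somewhat conservative. This mismatch needs no assumption about centres.

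Centres may also differ. Part of the outcome is discretionary: after failure criteria are met, "a trial of NIV might be allowed according to the physician's preference" (section 3.8, Treatment Failure Criteria), and general care is given by each unit's attending physicians (section 3.9). A pooled test treats differences between centres, and predictable differences between patients, as noise.

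Power is what is at stake. The sample size gives 80% with no stated allowance for dropout, so a few points are worth having if they cost little.

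**Working it through.** **1. The plan's own figure.** Inputs: control rate 0.60, prone rate 0.45 and power 80% (section 4.3); alpha 0.05 (section 4.2). Assumed: two-sided test, 1:1 allocation, no dropout. The mean rate is 0.525.

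n per arm = [1.960 × √(2 × 0.525 × 0.475) + 0.842 × √(0.60 × 0.40 + 0.45 × 0.55)]² / 0.15² = [1.384 + 0.588]² / 0.0225 = 172.8, so 173 per arm and 346 in total. This matches the plan. (The bracket in section 4.3 starts from 80%, but 45% is 60% × 0.75. The slip does not affect 346.)

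**2. The unadjusted test when centres differ.** Trials of 346 patients were simulated (20,000 per cell) with 3 to 30 centres, normal centre effects on the logit scale (SD 0 to 1.0), marginal rates held at 60% and 45%, and randomisation ignoring centre. Chi-square power was 79-81% throughout, with type I error 4.3-5.0%.

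**3. A plausible between-centre spread.** The only related figure is the 40% to 77% intubation range across cited studies (section 4.3). On the logit scale this runs from −0.405 to 1.208, a width of 1.61. Read as ±2 SD it gives SD 0.40; read as ±1 SD, 0.81. It is a range across studies, so it can only guide the assumption.

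**4. CMH by centre, no pooling, randomisation unchanged.** Power (%), chi-square → CMH, unequal centres:

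| Centres | SD 0 | SD 0.4 | SD 0.8 |
|---|---|---|---|
| 6 | 79.4 → 79.8 | 80.3 → 81.2 | 80.7 → 84.5 |
| 12 | 79.4 → 78.9 | 79.5 → 80.2 | 80.2 → 83.8 |
| 30 | 79.1 → 76.4 | 79.3 → 77.9 | 80.0 → 81.9 |

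The standard error of each figure is about √(0.8 × 0.2 / 20,000) = 0.3 points. With 30 centres and SD 0, the loss ranged from 2.7 to 3.7 points over all runs.

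**5. Why many centres cost power.** A centre of m patients allocated without regard to centre contributes on average (m − 1)/4 to the CMH information instead of m/4. With K centres the effective total is about 346 − K. For K = 30 that is 316, or 158 per arm: z = (0.15 × √158 − 1.384) / 0.698 = 0.718, giving power of about 76.4%, in line with the simulation. For K = 10 it is 336, or 168 per arm: z = 0.802 and power of about 78.9%.

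**6. Alternatives to unpooled CMH** (3,200 trials per cell, standard error about 0.7 points, randomisation unchanged). Power (%):

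| Layout | SD | Chi-square | CMH, centres under 20 pooled | Random intercept |
|---|---|---|---|---|
| 30 equal | 0 | 79.6 | 79.7 | 79.8 |
| 30 equal | 0.4 | 80.1 | 80.4 | 81.8 |
| 30 equal | 0.8 | 79.2 | 79.4 | 82.8 |
| 30 unequal | 0 | 79.6 | 79.5 | 79.7 |
| 30 unequal | 0.8 | 79.8 | 81.7 | 83.1 |
| 10 unequal | 0.4 | 78.9 | 80.3 | 80.7 |
| 10 unequal | 0.8 | 80.2 | 83.6 | 83.8 |

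Type I error of the two adjusted methods was 4.3-5.7%. The random intercept lost no power in any cell run; pooled CMH lost at most about 1 point (10 centres, SD 0). The size rule matters. Thirty equal centres hold 346/30 = 11.5 patients each, so a threshold of 20 merges them all and one of 10 merges none. With the latter, CMH gave 77.5% against 79.0% at SD 0.

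**7. Baseline predictors.** Logistic adjustment for two covariates that predict nothing left power unchanged within simulation error (80.1% v 80.4%). As prognostic strength rose to a logit SD of 0.8 (joint AUC about 0.70), the gain grew from about 2 to 5 points. Type I error was 4.7-5.1%.

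**8. Severity.** Its effect was not simulated separately. As an analogy, when randomisation was balanced within centre but chi-square ignored centre, type I error fell to 3.1-3.6% at SD 1.0. The direction is conservative; the size for severity depends on how prognostic it is.

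**The case against.** The strongest reply is that nothing is broken: the sample size reproduces, the test delivers its stated power, and false positives are controlled. That stands, and it makes this an improvement and not a correction of an error.

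A reader might infer that centre adjustment is power to be had for nothing. The documents do not support that, because they do not say how many centres there are, and step 4 shows a loss with many small, similar centres. The objection counts against unpooled CMH. It does not count against the random intercept in the layouts tried.

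A reader might also take the 40% to 77% in section 4.3 as the variation to expect between centres. Those rates come from different cohorts and mix case mix and sampling error with any site effect. The trial's centres share eligibility rules, HFNC settings and failure criteria, so their spread may well be smaller.

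Nor is the event simply a local decision. Several failure criteria in section 3.8 are numeric and common to all centres; only part is discretionary.

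Finally, the covariate gain rests on assumed strength. The timings in section 3.5 are tied to HFNC, not randomisation, so a baseline respiratory rate needs a defined window. Both points stand.

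**Conclusion.** The point holds as one of efficiency. The general tests in section 4.2, taken to apply to the primary outcome because no other is named, leave out the randomisation stratum, centre and baseline predictors. It would be wrong to conclude that the planned test is invalid or that the trial misses its 80% target for this reason.

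The size is modest. Baseline adjustment gains about 0 to 5 points (assumed logit SD 0 to 0.8). Centre adjustment gains about 0 to 4 points with around 10 centres (assumed between-centre SD 0 to 0.8), while unpooled CMH loses about 3 points with around 30 similar centres. The two gains were simulated separately and should not be added. The case for including severity rests on the design alone. The change is worth making, but the trial does not stand or fall by it.

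**What to change.** Leave randomisation unchanged and amend section 4.2 before database lock:

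- Name the primary between-arm analysis: a logistic model with treatment, ARDS severity as stratified, age, the last respiratory rate recorded before randomisation, and a random centre intercept.
- Define the time window for that respiratory rate.
- Report the standardised 28-day risk difference and risk ratio with 95% confidence intervals, since the model's odds ratio is conditional on the covariates.
- Do not use CMH by centre unless small centres are pooled by a size rule fixed before lock.
- Keep the unadjusted chi-square as a sensitivity check, and stratify the log-rank test by severity.
- State the number of centres.

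The cost is SAP wording, a slightly longer model and the window definition. The vital signs and patient characteristics are already due to be collected.

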1.2. Hypothesis / Key Questions

We hypothesize that early use of PP combined with HFNC can avoid the need for intubation in moderate to severe ARDS patients. The purpose of this RCT will be to evaluate the effects of PP combined with HFNC for improving oxygenation and reducing the need for intubation

compared with HFNC support alone, as well as the safety of the PP therapy in non-intubated COVID-19 induced ARDS patients.

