1.4. Secondary Objectives

The secondary outcomes for the efficacy of PP combined with HFNC will be the improvement of SpO_2/FiO_2 or PaO_2/FiO_2 from HFNC alone to HFNC+PP. SpO_2/FiO_2 will be utilized to substitute PaO_2/FiO_2 as a means for evaluating oxygenation.¹¹⁻¹⁴ As a practical substitute to PaO_2/FiO_2 , SpO_2/FiO_2 has been shown to have a strong linear relationship in moderate to severe ARDS¹⁴ and was recommended as a diagnostic tool for early enrollment in clinical trial.¹³ F_iO_2 will be titrated to maintain SpO_2 at 90-95%. Other secondary outcomes including the time duration for PP therapy, patients' comfort with PP, PP complications including skin break down, tube/I.V. dislodgement, and the threshold of SpO_2/FiO_2 for successful PP in COVID-19 induced ARDS cases, HFNC duration, ICU length of stay and ICU mortality rate.

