3.5. HFNC treatment

HFNC will be initiated at 50 L/min (AIRVO2 or Optiflow, Fisher &Paykel Health care Limited., Auckland, New Zealand) with temperature set at 37 °C. Nasal cannula size should be \leq

50% of the patient's nostril size. $F_{I}O_2$ will be adjusted to maintain SpO_2 at 90% to 95%. Flow and temperature will be adjusted based on patient's comfort and clinical response. Patients' vital signs, SpO_2 , oxygen device and $F_{I}O_2$ before HFNC will be recorded, Patients' vital signs, SpO_2 , HFNC flow and $F_{I}O_2$ at 30 mins, and 2 hour of HFNC will also be recorded for both groups. HFNC will be continuously delivered after enrollment in the study for ≥ 16 hours a day in the first 3 days. Patient comfort to HFNC, will be assessed by means of a scale used and validated in previous studies that is defined as follows: 1, bad; 2, poor; 3, sufficient; 4, good; 5, very good. Patients' vital signs, SpO_2 , HFNC flow and $F_{I}O_2$, as well as patient comfort will be documented every 4-6 hours. In order to prevent virus transmission, all the patients with HFNC treatments will wear a surgical mask over the face.¹⁶

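### The oxygenation outcome is worded as a before-after change with a paired ANOVA for time points, and the plan does not say whether that or a between-arm test is the efficacy analysis

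*Combined protocol and SAP*

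**What the plan says.** Section 1.4 puts oxygenation first among the secondary efficacy outcomes, as "the improvement of SpO_2/FiO_2 or PaO_2/FiO_2 from HFNC alone to HFNC+PP". It gives no time point and no control-arm counterpart.

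Section 4.2 handles repeated measurements in one sentence: "ANOVA for paired tests to compare the same variables collected at different time points are used". The same paragraph says that continuous variables "are compared using the unpaired Student's t test or the Mann-Whitney test" between the two groups, and closes with "All analyses are in intention to treat, and the level of significance is set at 0.05". No sentence assigns any of these tests to SpO2/FiO2 or PaO2/FiO2.

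Section 1.2 states the purpose, oxygenation included, as a comparison between arms: "compared with HFNC support alone, as well as the safety of the PP therapy in non-intubated COVID-19 induced ARDS patients".

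On data, section 4.1 lists "The respiratory assessments before, during the treatments of HFNC or HFNC with prone position". Section 3.5 records SpO2, flow and FiO2 "at 30 mins, and 2 hour of HFNC will also be recorded for both groups", and then every 4 to 6 hours. Neither section plans respiratory assessments after intubation, and no rule covers oxygenation values missing after intubation, non-invasive ventilation, death or withdrawal.

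**The concern.** Patients in the control arm never move to HFNC plus PP. Taken literally, the section 1.4 outcome can be computed only in the PP arm, and the paired method in section 4.2 suits exactly that computation. The result would not answer the section 1.2 question, which is how oxygenation compares with HFNC alone.

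Two biases are at stake.

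- **Uncontrolled change.** Patients enter because oxygenation is poor (section 2.1), so a repeat reading tends to be higher with no treatment effect. Disease course and the antivirals and steroids recorded under section 3.9 also act on any before-after change.
- **Selective loss.** If later readings exist only for patients still on HFNC, and the arms are intubated at different rates, the patients left in the two arms are no longer comparable. This affects an unpaired between-arm test too.

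The randomised control arm removes the first bias in expectation, provided that the analysis uses it.

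**Working it through.** **The plan's own figure.** Section 4.3 gives 346 patients for 60% against 45% intubated, 80% power and a 5% level. I take the test as two-sided and the allocation as 1:1, since neither is stated. With the pooled-variance formula and mean proportion 0.525:

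n per arm = [1.960·√(2·0.525·0.475) + 0.842·√(0.60·0.40 + 0.45·0.55)]² / 0.15² = 172.8, rounded up to 173, so 346 in total.

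This matches. It concerns intubation only; the plan gives no size calculation for oxygenation.

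**Inputs not in the documents.** The SD of SpO2/FiO2, its test-retest correlation, the mean in the screened population, and the correlation between oxygenation and avoiding intubation are all assumed. The results are illustrations.

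**Step 1: regression to the mean in a before-after test.** Assume SD 50 and no PP effect, with the qualifying value as the baseline. Entry is restricted to 90 up to 240, from the SpO2/FiO2 exclusion limit in section 2.2 and the upper bound of the moderate class in section 2.1. For screened mean μ and test-retest correlation r, let a = (90 − μ)/50 and b = (240 − μ)/50. Then

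expected change = (1 − r)·50·[φ(b) − φ(a)] / [Φ(b) − Φ(a)].

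| μ | bracketed ratio | r = 0.6 | r = 0.75 | r = 0.9 |
|---|---|---|---|---|
| 180 | 0.136 | +2.7 | +1.7 | +0.7 |
| 200 | 0.328 | +6.6 | +4.1 | +1.6 |
| 220 | 0.545 | +10.9 | +6.8 | +2.7 |
| 240 | 0.791 | +15.8 | +9.9 | +4.0 |

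The range is about +1 to +16 units. Simulated SDs of the change were 22.1 (μ = 180, r = 0.9) and 41.7 (μ = 240, r = 0.6). With 173 patients, a nominal 5% paired test is then significant in about 7% of trials in the mildest case and over 99% in the most extreme.

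If the baseline is instead a new reading taken just before proning, and all readings are equally correlated, selection on the qualifying value shifts both later readings equally. The expected change is then zero.

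**Step 2: loss to intubation in a later between-arm comparison.** At the section 4.3 rates, 0.40·173 ≈ 69 HFNC patients and 0.55·173 ≈ 95 PP patients are never intubated. Let ρ be the assumed correlation between follow-up oxygenation and staying unintubated, and let p be the proportion intubated. The mean of those remaining is raised by ρ·50·φ(z_p)/(1 − p), where z_p is the p quantile of the standard normal.

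- HFNC, p = 0.60: φ(z_p)/(1 − p) = 0.966, so a rise of 14.5 (ρ = 0.3) to 33.8 (ρ = 0.7).
- PP, p = 0.45: 0.720, so a rise of 10.8 to 25.2.
- PP minus HFNC: (0.720 − 0.966)·50·ρ = −0.246·50·ρ, which is −3.7 to −8.6.
- At half those rates (30% and 22.5%): (0.387 − 0.497)·50·ρ = −0.110·50·ρ, which is −1.6 to −3.8.

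In simulation at the full rates, a true benefit of +10 units appeared as about +6.5 (ρ = 0.3) to +1.3 (ρ = 0.7).

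**Step 3: timing.** The 30-minute and 2-hour readings in section 3.5 count from the start of HFNC. Section 2.1 enrols patients already on HFNC, and section 3.2 allows up to 6 hours from meeting the criteria to randomisation. The 2-hour reading may therefore precede randomisation and any proning. The 4-to-6-hourly records can be aligned to randomisation.

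**The case against.** A reader might infer that the plan tests oxygenation only before against after, and only in patients still on HFNC. The documents do not support that. The paired ANOVA sentence sits in the paragraph on comparisons between the two groups, after the unpaired t and Mann-Whitney tests. Section 1.2 states a between-arm purpose, and section 4.2 declares intention to treat. No sentence restricts the analysis to patients remaining on HFNC; that is only a plausible consequence of when data are collected. So the plan is ambiguous about the test and silent on missing values, and it does not state a wrong rule.

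The sizes can also be challenged, with some force. The upper regression-to-the-mean figures need a screened population near the entry limit and the qualifying value as baseline. Natural worsening could offset or reverse the rise, so a before-after change need not overstate PP. The 60% and 45% are the full planned intubation rates, and section 3.8 sets the primary endpoint at 28 days. Few patients would be lost within one prone session or the first hours. Other losses may act differently: weaning (section 3.7) removes the best patients, and withdrawal for prone intolerance (section 3.6) can occur only with PP.

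These points limit the size and certainty of the bias, but they do not settle which test is the efficacy test. An unpaired test avoids the first bias but not the second. An intention-to-treat statement cannot supply values that nobody plans to record.

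**Conclusion.** The point holds as an ambiguity with a missing rule. The outcome is worded as a within-patient change that controls cannot have, the only method for time points is paired, and nothing says whether that or the unpaired test is the efficacy analysis.

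If the before-after result were reported as efficacy, regression to the mean could contribute from near zero (fresh pre-prone baseline) to about +16 SpO2/FiO2 units, alongside disease course and co-treatment. If later comparisons used only patients still on HFNC, the bias could be about 4 to 9 units against PP at the full planned intubation rates and about 2 to 4 at half of them, with little in the first hours. All of these rest on the assumed means, SD of 50 and correlations above.

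This is a secondary outcome. Neither the primary endpoint nor the 346 patients is affected.

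**What to change.** In sections 1.4 and 4.2, define the oxygenation efficacy analysis as a comparison of all patients as randomised:

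- Use ANCOVA, or a mixed model with an arm-by-time term, adjusted for SpO2/FiO2 at randomisation and the severity stratum.
- Prespecify one early time point, counted from randomisation and taken from the existing 4-to-6-hourly records, not the reading 2 hours after HFNC start.
- Add a sensitivity analysis that ranks patients intubated or dead by that time as worst.
- Report paired before-after results in the PP arm as descriptive only.

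The SpO2 targets also differ: 90–95% in sections 1.4 and 3.5, 92–95% during PP in section 3.4, and 88–93% in the enrolment criterion of section 2.1. They affect the ratio being analysed and must be reconciled.

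The cost is revised wording and modest extra programming. No new data are needed, and the sample size stays at 346.
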